6.5 Handling of Dropouts and Missing Data

With the exception of the scenarios covered in this section, missing data will not be imputed.

AE dates will be imputed for the purpose of calculating duration of events and treatment-emergent status (see Appendix A for imputation details and Appendix B for treatment-emergent definition). Censoring will be described in Section 7 with each planned analysis, as applicable.

Unless otherwise specified, lab values which are recorded or provided as being less than x.x will be included in figures and summaries as x.x/2. For the purpose of grading, lab values reported as less than x.x will be imputed as x.x.

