5.8 Dose Modifications

Dose modifications of rituximab, etoposide, ifosfamide, or carboplatin due to hematologic and non-hematologic toxicity are allowed per institutional standards and according to the product-specific United States Prescribing Information (USPI), or other country-specific package insert, at the discretion of the investigator. Permitted dose modifications include discontinuation of a treatment component.

Myelosuppression is an expected consequence of RICE chemo-immunotherapy and should not be used as the basis for dose reduction or elimination of denintuzumab mafodotin. All patients should receive growth factor support to shorten the duration of neutropenia (see Section 5.4). If adequate myeloid recovery has not occurred per institutional standard of care, initiation of the next cycle may be postponed. Cycle 2 and/or Cycle 3 should not begin until there has been satisfactory recovery of peripheral blood counts (i.e., recommend that platelets $\geq 75,000/\mu\text{L}$ and ANC $\geq 1000/\mu\text{L}$).

If RICE chemo-immunotherapy will be delayed at the start of Cycle 2 or Cycle 3 due to myelosuppression or other dose-delaying toxicity (DDT), denintuzumab mafodotin infusion will be delayed as well. A delay of more than 14 days in starting RICE in Cycles 2 and/or 3 is discouraged; delays of more than 21 days are not allowed without discussion with the sponsor.

If RICE chemo-immunotherapy is discontinued, no further denintuzumab mafodotin will be given and the patient will be discontinued from the treatment phase of the study (see Section 6.6).

Denintuzumab mafodotin infusion may be delayed at the start of Cycle 2 or Cycle 3 due to ocular toxicity (see Section 5.8.1). Per-patient dose modifications of denintuzumab mafodotin are permitted as described in Section 5.8.1. Dose modifications of denintuzumab mafodotin must be discussed with the medical monitor. In the absence of myelosuppression

or other DDT, RICE chemo-immunotherapy should be administered as planned on a q3week (21-day) cycle.

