Hospitalization:	The AE required or prolonged an existing inpatient hospitalization. Hospitalizations for elective medical or surgical procedures or treatments planned before the signing of informed consent in the study or routine check-ups are not SAEs by this criterion. Admission to a palliative unit or hospice care facility is not considered to be a hospitalization. Hospitalizations or prolonged hospitalizations for scheduled therapy of the underlying cancer or study target disease need not be captured as SAEs.
Disabling/ incapacitating:	Resulted in a persistent or significant incapacity or substantial disruption of the patient's ability to conduct normal life functions.
Congenital anomaly or birth defect:	An adverse outcome in a child or fetus of a patient exposed to the molecule or study treatment regimen before conception or during pregnancy.
Medically significant:	The AE did not meet any of the above criteria, but could have jeopardized the patient and might have required medical or surgical intervention to prevent one of the outcomes listed above or involves suspected transmission via a medicinal product of an infectious agent.

Adverse Event Severity

AE severity should be graded using the National Cancer Institute's Common Terminology Criteria for Adverse Events (NCI CTCAE), version 4.03, with the exception of ocular adverse events which will be graded according to a modified CTCAE version 4.03 scheme ([Appendix E](#)). The NCI CTCAE, version 4.03 criteria are provided in the study manual or may be accessed at <http://ctep.cancer.gov/reporting/ctc.html>.

AE severity and seriousness are assessed independently. 'Severity' characterizes the intensity of an AE. 'Serious' is a regulatory definition and serves as a guide to the sponsor for defining regulatory reporting obligations (see definition for Serious Adverse Events).

Relationship of the Adverse Event to Study Treatment

The relationship of each AE to each study treatment (denintuzumab mafodotin or RICE) should be evaluated by the investigator using the following criteria:

Related:	There is evidence to suggest a causal relationship between the drug and the AE, such as: 
• an event that is uncommon and known to be strongly associated with drug exposure (e.g., angioedema, hepatic injury, Stevens-Johnson Syndrome)• an event that is not commonly associated with drug exposure, but is otherwise uncommon in the population exposed to the drug (e.g., tendon rupture)

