7.6 Safety Analyses

The Safety analysis set will be used to summarize all safety endpoints.

Adverse events will be coded using Medical Dictionary for Regulatory Activities (MedDRA, Version 18.0 or higher).

Laboratory values will be graded according to the National Cancer Institute (NCI) Common Terminology Criteria for Adverse Events (CTCAE version 4.03 or higher).

Concomitant medications will be coded using WHO Drug (version: June 2015 or more recent).

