7.6.2 Clinical Laboratory Parameters

Blood

Clinical laboratory data (CBC with differential, serum chemistry) may be presented graphically for selected lab tests by scheduled visit. Summary statistics may be tabulated where appropriate. The worst post baseline NCI CTCAE v4.03 grade will be presented for each lab test.

Laboratory results and NCI CTCAE grades for hematology, and serum chemistry will be presented in data listings. All laboratory data will be presented in conventional units.

Urine

UPC ratio will be presented graphically by scheduled visit. All other urine parameters will be listed.

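### SAP 6.5 grades a lab result reported as 'less than x.x' at x.x, so a low count is graded too mildly when x.x sits on a CTCAE cut-off, and possibly when it lies above one

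*SAP*

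**What the plan says.** SAP 6.5 makes two substitutions for a result known only to be below x.x. For display, such a value "will be included in figures and summaries as x.x/2". For toxicity grading the next sentence reads: "For the purpose of grading, lab values reported as less than x.x will be imputed as x.x". No reason is given for using two values. The grading rule is the same for every test and does not ask whether low or high values are the abnormal ones.

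The grade then feeds a firm output. SAP 7.6.2 states: "The worst post baseline NCI CTCAE v4.03 grade will be presented for each lab test". Graphs and summary statistics of laboratory values are only optional in that section. Grades also appear in the data listings.

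Protocol 7.7.3 has the tests done by local laboratories and states no reporting limit for any of them. The CTCAE limits are not reproduced either; Protocol 7.7.1.1 says that the "version 4.03 criteria are provided in the study manual".

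**The concern.** A result below x.x cannot equal x.x. Where low counts are the toxicity, grading at x.x uses the most favourable end of the range, and any error goes towards milder toxicity.

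This matters for three reasons.

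- The severity of laboratory abnormalities is a named secondary endpoint (Protocol 2.4.2, SAP 3.2).
- Low counts are expected in both arms: "Myelosuppression is an expected consequence of RICE chemo-immunotherapy" (Protocol 5.8). Protocol 1.4 names transient thrombocytopenia as an effect consistently seen with the study drug, and the dose rationale in Protocol 3.2.2 itself relies on counts of Grade 3/4 haematological events.
- Adverse event data do not fully duplicate the lab grades. Under Protocol 7.7.1.1 an abnormal value generally becomes an adverse event only if it has symptoms, needs intervention, is serious, or affects treatment or study participation.

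**Working it through.** The plan states no figure to reproduce, so the check is of the rule's logic.

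**Inputs from the documents.** A result '<x' is graded at x and summarised at x/2 (SAP 6.5). Each test's worst grade after baseline is tabulated (SAP 7.6.2). Reporting limits and blood-count cut-offs are not given.

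**Assumed scale, for illustration only.** Let c be the worst-grade (Grade 4) cut-off, and place the four cut-offs at c, 2c, 3c and 4c, each defined as strictly 'below'. The grade of a value is then the number of cut-offs strictly above it. The spacing is arbitrary; the pattern depends only on where x falls relative to the cut-offs.

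| Reporting limit x | SAP rule (grade at x) | Just below x | At x/2 | Near 0 | Possible true grade |
|---|---|---|---|---|---|
| 0.1c, 0.5c, 0.9c, 0.99c | 4 | 4 | 4 | 4 | 4 |
| 1.0c | 3 | 4 | 4 | 4 | 4 |
| 1.5c | 3 | 3 | 4 | 4 | 3 or 4 |
| 2.0c | 2 | 3 | 3 | 4 | 3 or 4 |
| 2.5c | 2 | 2 | 3 | 4 | 2 to 4 |
| 3.0c | 1 | 2 | 3 | 4 | 2 to 4 |

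Reading the rows:

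1. With x below c, every substitution gives the same grade. The rule changes nothing.
2. With x on a cut-off (1.0c, 2.0c, 3.0c), the SAP grade is outside the possible range. It is at least one grade too low, whatever the true value.
3. With x between cut-offs (1.5c, 2.5c), the SAP grade is the mildest possible one. It may be right, or one or two grades too low.
4. Using x/2 throughout is not a clean repair. At 1.5c it assigns Grade 4 (0.75c is below c) although the true grade may be 3.

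**High-direction tests.** With assumed cut-offs at 1, 2, 3 and 4, and the grade equal to the number of cut-offs strictly below the value, x = 1.5 gives Grade 1 at x and Grade 0 at x/2. For x = 2.5 the grades are 2 and 1. Here x is the most severe bound, so the SAP rule cannot understate the grade, and replacing x by x/2 would remove that protection.

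**The case against.** The strongest reply is that nothing in the documents shows the triggering condition occurring. A wrong grade needs a reporting limit at or above a cut-off, and no limit is stated for any local laboratory. If all limits lie below the worst-grade cut-off, no grade changes. This stands, and it rules out any claim about size. It does not defend the rule: limits at local laboratories are not controlled by the plan, so the SAP cannot presume they are all low enough.

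The second reply is that marrow toxicity is also seen elsewhere: dose-delaying toxicity reviewed by the safety monitoring committee (Protocol 3.1.1, 3.1.2), Grade 3 to 5 treatment-emergent events (SAP 7.6.1), stem cell mobilization (SAP 7.5.2.6), transfusion and G-CSF use (SAP 7.6.5) and engraftment (SAP 7.6.6.4). Safety also carries no formal hypothesis (Protocol 9.3.1). This also stands and limits the importance of the point. None of those outputs replaces the lab-grade table.

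A reader might infer more than the documents support:

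- *That severe cytopenia is under-reported here and the arm difference shrunk.* Let p be the true Grade 4 rate in an arm and s the share of those patients whose grade rests only on a '<x' result with x at or above c. The tabulated rate is p(1 − s). The documents give neither p nor s, and s may be 0. With a common s the arm difference is multiplied by (1 − s); with unequal s it could shrink or widen.
- *That one result appears at two grades.* SAP 6.5 uses x/2 only as a value in figures and summaries. No planned output grades it. At most, a plotted value may imply a different grade from the one tabulated.
- *That all laboratory tests are biased towards mild grades, or always by one step.* The first fails for high-direction tests; the second fails because the error can be zero or more than one grade.

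**Conclusion.** The point holds for low-direction grading only. SAP 6.5 assigns a low count a value it cannot have. The grade is certainly too low when the reporting limit equals a cut-off defined as 'below', may be too low when the limit lies above a cut-off, and is unaffected when the limit lies below the worst-grade cut-off.

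The certain case rests on cut-offs being strict; if a cut-off were defined as 'at or below', grading at x.x would give the right side of it. The size in this trial cannot be computed from the documents. The reach is confined to lab-grade tables and listings: the CR analysis does not use these grades, and cytopenias that qualify as adverse events are graded separately by the investigator. The direction is certain and the size unknown. Because removing the error is nearly free, the rule should be changed before database lock.

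**What to change.** Replace the grading sentence in SAP 6.5 with:

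> For low-direction grading, a result reported as less than x.x will be graded as a value strictly (just) below x.x; for high-direction grading, x.x will be used. Any such result whose grade could differ across the possible range will be listed.

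Tests that can be abnormal in either direction are handled by applying each half of the rule to its own direction. The first clause removes the impossible grades that arise when x.x sits on a cut-off. It leaves the grade unchanged when x.x lies between cut-offs, so the listing is needed to show that remaining uncertainty. The x.x/2 rule for figures and summaries can stay.

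The cost is one SAP sentence, a line of derivation code, a short listing and possibly a slightly less favourable severe cytopenia rate.

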6.6 Pooling Strategy for Strata

The randomization of this study is stratified by 3 factors with a total of 8 strata. In situations where a stratum cannot be included in a stratified analysis of an endpoint, it may be necessary to pool strata prior to the analysis. For example, strata will be pooled if no patients are randomized under a stratum. Should pooling be necessary, it will be performed in the following order:

1. Do not include the stratification factor of Disease Type, i.e. De novo DLBCL and Grade 3b follicular lymphoma (G3bFL) will be pooled with Transformed DLBCL for each combination of other two stratification factors
2. Only include the stratification factor based on the saaIPI or standard IPI score: Low-risk disease (saaIPI of 0 or 1, or standard IPI of 0, 1, or 2) vs. High-risk disease (saaIPI of 2 or 3, or standard IPI of 3, 4, or 5)
3. If further pooling is necessary, no stratified analysis will be performed.

6.7 Multicenter Studies

There are multiple centers in this study, however it is not anticipated that any center will accrue enough patients to warrant an analysis by center.

6.8 Multiple Comparison/Multiplicity

A fixed sequence testing procedure (Westfall 2001), where testing is carried out sequentially at an unadjusted alpha level as long as all preceding null hypotheses are rejected, will be used to ensure type I error control for key secondary endpoints. The testing order will be: 1) CR rate per IRF; 2) PFS per investigator assessment; and 3) duration of CR per investigator assessment. If the test for CR rate is not statistically significant, the p-value of the tests for the subsequent endpoints will still be calculated, but will be considered descriptive.

6.9 Examination of Subgroups

As exploratory analyses, subgroup analyses may be conducted for selected endpoints. Subgroups may include but are not limited to the following:

- Disease status ([CR to frontline systemic therapy and relapsed >12 months after initial diagnosis] versus [PR or SD to frontline systemic therapy, or CR to frontline and relapsed ≤12 months after initial diagnosis])
- Disease risk as determined by standard IPI or saalPI
- Disease type (De novo DLBCL/G3bFL versus Transformed DLBCL)
- Cell of origin by gene expression profiling (GEP)
- Double- and triple- hit lymphoma
- Double expresser lymphoma
- CD19 expression
- CD20 expression
- Minimum Residual Disease (MRD) status
- Age (18- 64 vs. ≥ 65years; and/or < 60 vs >60 years)
- Gender
- Baseline ECOG
- Disease stage
- Patients with and without post-baseline consolidative ASCT

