PET scans and computed tomography (CT) scans of the neck, chest, abdomen, and pelvis, will be assessed at baseline and at end of treatment (EOT). CT scans will be of diagnostic quality (i.e., contrast-enhanced with IV and oral contrast, unless contrast is medically contraindicated). Follow-up assessments will be performed at 3, 6, 12, 18, 24 months, and then annually after ASCT or EOT (for patients who don't receive ASCT). For all follow-up assessments, both PET and CT scans are required until disease is PET negative; responses will then be followed by CT scans of diagnostic quality. Follow-up assessments will continue until disease progression, initiation of a new anticancer treatment (with the exception of a stem cell transplant), or study closure, whichever occurs first.

At screening and/or at any time on study, if a bone marrow biopsy is performed as part of standard of care, the results from the biopsy report for the presence of lymphoma will be recorded in the case report form (CRF). A CT scan of diagnostic quality will be performed at the time of suspected clinical progression. Survival status follow-up will continue until patient death or study closure, whichever occurs first.

Subsequent ASCT is permitted, based on investigator discretion and standard of care, and is recommended to occur within 8 weeks of Cycle 3 Day 1 (Philip 1995). Data will be recorded to assess adequacy of hematopoietic stem cell collection and transplant.

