7.4.2 Protein Markers in Blood

Serum and plasma will be obtained and evaluated for soluble mediator quantification. Soluble CD19 is elevated in autoimmune disorders. The level of sCD19 in DLBCL patients at baseline may be predictive of denintuzumab mafodotin treatment response. sCD19 may be measured pre- and post-treatment with denintuzumab mafodotin to understand its value as a potential predictive marker as well as a pharmacodynamic marker. Circulating proteins related to tumor burden or other potentially prognostic characteristics of the disease will also be monitored. In addition, Minimal Residual Disease (MRD) evaluation may also be carried out to understand the depth of response to therapy and correlate with PFS and other patient outcomes. Molecular MRD status may be analyzed using the Adaptive ClonoSEQ assay.

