6 STATISTICAL CONSIDERATIONS

6.1 General Principles

Descriptive statistics (mean, median, standard deviation, minimum and maximum) will be used to summarize continuous variables. Frequencies and percentages will be used to summarize categorical variables. The median survival time will be estimated using the Kaplan-Meier method; the associated confidence interval (CI) will be calculated based on the complementary log-log transformation (Collett 1994). All summaries will be presented by treatment arm and total unless otherwise specified. If the dose of denintuzumab mafodotin is decreased from 3mg/kg to 2 mg/kg, summaries for each level of denintuzumab mafodotin and subtotal will be presented.

Unless otherwise specified, all statistical tests will be performed using a two-sided alpha of 0.1. Confidence intervals will be calculated at a two-sided 90% level. Multiplicity adjustment for alpha level is discussed in Section 6.8.

Any analysis not described in this plan will be considered exploratory, and will be documented in the clinical study report (CSR) as a post hoc analysis or a change to the planned analysis.

To comply with regulatory electronic submission guidelines, listings of all clinical data will be submitted as electronic data sets. To facilitate data review for the study report, only pertinent data listings will be created and attached to the appendix of the CSR.

All statistical output will be produced using SAS[®], version 9.3 or more recent. Other statistical software, if used, will be described in the CSR.

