6.2 Determination of Sample Size

A total of approximately 100 patients (approximately 50 patients per treatment arm) will be enrolled and randomized to a treatment arm in this study.

With approximately 100 patients randomized in a 1:1 ratio to each treatment arm (~50 patients per arm), the study is designed to have approximately 80% power to detect an increase in the CR rate of 25%. It is assumed that the CR rates for the 19A+RICE Arm and the RICE Arm are 60% and 35%, respectively. This calculation is based on a two-sided χ^2 test with significance level of $\alpha=0.1$ using EAST (version 5.4).

If the dose of denintuzumab mafodotin in the investigational 19A+RICE arm is modified, up to 50 additional patients may be randomized (25 in each arm) so that a total of 100 patients will be randomized in a 1:1 ratio to either the 19A (modified dose) + RICE arm or the RICE only arm. Up to approximately 150 patients may be randomized in this study.

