Kaplan-Meier Curves depicting PFS in the two arms will be generated. Additionally, median PFS and probability of PFS will be reported at 6 month intervals. The two-sided 90% confidence intervals (CI) for the median will be calculated using the complementary log-log transformation method (Collett 1994).

The primary analysis of PFS will be performed based on investigator assessment. PFS may be performed for each of the subgroups specified in Section 6.8.

Cox regression of PFS will be used to estimate the hazard ratio of 19A+RICE to RICE. The baseline covariates specified in Section 6.9 may be included in the model. The treatment group variable will always be included in the model. Interaction effects may be considered whenever possible.

Secondary Analysis for PFS

The censoring rule for PFS based on IRF assessment is presented in Table 2 as follows:

Table 2: PFS Event Rules for Secondary PFS Analysis (IRF Assessment)

Situation	Date of Progression or Censoring	Outcome
No baseline and/or post-baseline assessment	Date of randomization	Censored
Documented progression documented between scheduled visits	Date of documented progression ^a	Event
New anticancer therapy initiated prior to documented progression or without documented progression or death, with the exception of post treatment consolidative radiotherapy, or post treatment chemotherapy for the purpose of mobilizing PBSCs, or ASCT	Start date of new anticancer therapy	Event
Death before first documented progression and new anticancer therapy	Date of death	Event
No progression, new anticancer therapy or death	Date of last adequate assessment ^{a,b}	Censored

a Determined by IRF based on IRF charter

In this analysis, investigator claim of clinical progression that is not confirmed by IRF assessment at the same visit will not be regarded as having a progression event.

Sensitivity Analyses

Sensitivity analyses of PFS will be performed. Sensitivity analyses may include, but will not be limited to, the following

1. For patients with new anticancer therapy initiated prior to documented progression, PFS will be censored at the date of last adequate assessment prior to the new therapy.
2. An unstratified log-rank test will be used to compare the PFS by investigator between the treatment groups. PFS will be censored according to Table 1. Additionally, an unstratified Cox regression model will be used to estimate the hazard ratio and the corresponding 90% CI for the treatment effect.

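### The SAP lists receipt of ASCT and MRD status, which treatment can change, as PFS subgroups beside baseline factors, with no landmark or caution

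*SAP*

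**What the plan says.** SAP 6.9 gives one list of exploratory subgroups. Most entries are baseline factors such as disease status, risk score, age, gender and stage. Two are not plainly so: "Minimum Residual Disease (MRD) status", with no timepoint, and "Patients with and without post-baseline consolidative ASCT", which is post-baseline by its own wording.

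SAP 7.5.2.1 defines PFS from randomisation and states that "PFS may be performed for each of the subgroups specified in Section 6.8". Section 6.8 is the multiplicity section; the subgroup list is in 6.9, so 6.9 is evidently meant. SAP 7.5 has the same slip. SAP 7.5.2.1 also refers to baseline covariates in 6.9, where 6.10 is evidently meant.

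Protocol 7.4.2 says MRD may be evaluated "to understand the depth of response to therapy and correlate with PFS" and other outcomes. Receipt of ASCT is a secondary endpoint (SAP 3.2). Under Protocol 9.2.2.5 it counts only after study treatment and before subsequent anticancer therapy, which is itself a PFS event. Protocol 3.1 says ASCT "is recommended to occur within 8 weeks of Cycle 3 Day 1".

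Neither document gives a landmark, a time-dependent covariate, a delayed-entry rule or a caution for these two subgroups. The protocol's own open-ended subgroup list (9.3.1.8) names only disease status, risk group, disease type and cell of origin.

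**The concern.** A subgroup analysis keeps the protection of randomisation only if subgroup membership is fixed before treatment can act on it. Here it is not.

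**Selection on a treatment-affected variable.** The trial is built on the hope that 19A+RICE produces more complete remissions. If it does, it will probably also produce more MRD-negative patients and more transplants. The MRD-negative (or transplanted) patients in the two arms are then different mixtures of prognosis, and an arm comparison among them is no longer randomised. The same holds in the complementary stratum.

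**Immortal time.** A patient who dies or starts new therapy early cannot enter the ASCT group as Protocol 9.2.2.5 defines it. Counted from randomisation, those early PFS events all fall in the no-ASCT group, so ASCT looks protective even if it does nothing.

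At stake is interpretation: a spurious benefit of transplant, and a distorted treatment effect within strata that readers of a lymphoma trial will want to see.

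**Working it through.** **1. The plan's own figure.** SAP 6.2 says "the study is designed to have approximately 80% power to detect an increase in the CR rate of 25" percentage points, and that "It is assumed that the CR rates for the 19A+RICE Arm and the RICE Arm are 60% and 35%, respectively". SAP 6.1 says "Unless otherwise specified, all statistical tests will be performed using a two-sided alpha of 0.1". With 50 per arm and mean rate 0.475:
- standard error under the null: √(2 × 0.475 × 0.525 / 50) = 0.0999
- standard error under the alternative: √((0.35 × 0.65 + 0.60 × 0.40) / 50) = 0.0967
- power = Φ((0.25 − 1.645 × 0.0999) / 0.0967) = 81.2%; exact Pearson chi-square power is 79.9%

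The stated 80% reproduces. It does not depend on the subgroup list; its use here is to supply the 60% and 35% for step 4.

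**2. Timing.** With three-week cycles and no delay, Cycle 3 Day 1 is day 43.
- The EOT visit is 14 to 30 days after the start of the last cycle (Protocol 6.6): days 57 to 73, or 56/30.4375 = 1.84 to 72/30.4375 = 2.37 months after randomisation, taking randomisation as day 1.
- ASCT within 8 weeks of day 43 means up to day 99: 98/30.4375 = 3.22 months.

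**3. Immortal time, ASCT versus no ASCT.** The background figures are those of the salvage trial described in Protocol 1.1: median PFS about 1 year, and 50% proceeding to ASCT. Assumptions: exponential PFS, no ASCT effect, and all transplants at one time *t* (months) in patients still event-free.
- Overall six-month PFS: 0.5^(6/12) = 0.707
- ASCT group: 0.5^((6 − *t*)/12)
- No-ASCT group: (0.707 − 0.5 × ASCT value) / 0.5

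| Transplant day | *t* (months) | Event before *t* | ASCT | No ASCT |
|---|---|---|---|---|
| 57 | 1.84 | 10% | 79% | 63% |
| 73 | 2.37 | 13% | 81% | 60% |
| 99 | 3.22 | 17% | 85% | 56% |

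The same model was simulated with 24 to 48 months of follow-up and a Cox model from randomisation. At median 12 months, 50% transplanted and *t* = 3.2, the hazard ratio for ASCT versus none is 0.65 (medians 15.2 and 8.1 months), although the true value is 1. At *t* = 2.0 it is 0.76. Over medians of 6, 12 and 18 months, *t* of 2.0 or 3.2, and shares of 30%, 50% and 60%, it runs from 0.30 to 0.87. Starting the clock at the transplant time brings it back to 1.00 to 1.01 in every scenario.

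**4. Arm comparison within response-type strata.** Each simulated patient has a latent prognosis, uniform on 0 to 1. PFS depends on prognosis only, so there is no arm effect. The best 60% respond in the 19A+RICE arm and the best 35% in the RICE arm. Response stands in for MRD negativity or fitness for transplant.

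| Median PFS (months), best to worst prognosis | Overall arm HR | HR in responders | HR in non-responders |
|---|---|---|---|
| 36 to 4 | 1.00 | 1.31 | 1.33 |
| 24 to 6 | 1.01 | 1.20 | 1.20 |
| 18 to 8 | 1.00 | 1.11 | 1.11 |

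The extra responders on 19A+RICE have worse prognosis than the RICE responders and better prognosis than the remaining non-responders. They therefore worsen the 19A+RICE result in both strata. The spread of prognosis is an assumption; the documents give none.

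**5. Does immortal time apply to MRD?** Only in part. Protocol 6.6 schedules biomarker blood at EOT and covers patients who stop for progression; Table 3 lists whole blood, serum and plasma at EOT. A patient who progresses on treatment is therefore still due a sample. Those missing from an EOT-based MRD classification are patients who die, withdraw or miss the sample.

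**The case against.** **The analyses are optional and exploratory.** SAP 6.9 and 7.5.2.1 say they may be done, and they lie outside the fixed sequence in SAP 6.8. This stands and limits the consequence to interpretation. It does not make the analysis sound: exploratory status excuses imprecision, not a bias that can be foreseen.

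**The MRD timepoint is not documented.** This stands. Table 3 has blood draws from before the first dose through EOT, and Protocol 9.3.7 leaves biomarker details to separate plans that are not in these documents. That MRD status is post-treatment is inferred from its description as depth of response.

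**Summaries are by arm, so the implied comparison is arm against arm within strata, not ASCT against none.** Largely fair. The figures in step 3 of the working apply only if the two ASCT groups are set against each other, which a side-by-side display invites. Step 4 addresses the comparison by arm.

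**The sponsor already knows the hazard.** Protocol 3.2 names the decision to proceed to transplant as a possible source of bias when justifying CR as primary endpoint. True, but no safeguard follows for this subgroup.

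A reader might go further and infer that a patient must be event-free to have an MRD result. The EOT sampling schedule does not support that. A reader might also take 85% versus 56% as the expected size. It is the end of the recommended transplant window under one assumed curve.

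**Conclusion.** The point holds, at moderate weight. As written, the SAP permits PFS from randomisation within strata that treatment can change, with no safeguard.

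- Arm comparisons within the strata: a null effect could appear as a hazard ratio of about 1.1 to 1.3 against 19A+RICE. Size and direction rest on the latent-prognosis model and on CR rates of 60% and 35%.
- ASCT versus no ASCT: a null effect could appear as a hazard ratio of about 0.65 for transplant near day 99, with a range of 0.30 to 0.87 over the assumed inputs. This rests on exponential PFS and a single transplant time.
- MRD: the main fault is conditioning on response. Immortal time is limited to patients with no sample, and the point assumes a post-treatment measurement.

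It might be inferred that the trial's main conclusions are at risk. They are not: the primary CR test, the PFS and duration-of-CR tests in the fixed sequence, and the sample size do not use these subgroups.

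**What to change.** - Remove MRD status and post-baseline ASCT from the subgroup list in SAP 6.9.
- State the MRD timepoint, and report the MRD-negative rate by arm as a response outcome.
- Relate MRD to PFS from an EOT landmark, among patients event-free and sampled at that point.
- Describe ASCT and PFS in a separate landmark or time-dependent analysis, labelled descriptive, with no causal comparison of arms within strata.
- Keep ASCT out of the Cox model that estimates the treatment hazard ratio, even as a time-dependent term; there it would again condition the arm effect on something treatment can change.
- Correct the cross-references: 6.8 to 6.9 in SAP 7.5 and 7.5.2.1 for subgroups, and 6.9 to 6.10 in 7.5.2.1 for covariates. Read literally, the latter would admit ASCT and MRD as fixed covariates.

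The cost is SAP wording and one or two further exploratory analyses. ASCT and PFS dates are already collected, and EOT biomarker blood is already scheduled, although the MRD assay itself is optional. Protocol 9.3 requires a protocol amendment only for changes that alter site conduct, and this one does not. The downside is that a landmark drops patients with earlier events from that analysis. Neither a landmark nor a time-dependent term removes selection, hence the descriptive label.
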